#### 7.2.4 Additional secondary endpoints analyses

In MMRM analyses of square root transformed endpoints, the resulting means, difference and corresponding standard errors are back-transformed to the original scale using a second-order Taylor series expansion.

Let mean\_p, mean\_a, var\_p, and var\_a be the resulting means and variances for placebo and active treatment and cov be the covariance. Then the back-transformed means are given by

- mean\_placebo=(mean\_p)^2
- mean\_active=(mean\_a)^2
- mean\_difference=(mean\_a)^2-(mean\_p)^2,

and the back-transformed standard errors are given by

stderr\_difference=sqrt(4\*act\*\*2\*var\_act + 4\*pla\*\*2\*var\_pla + var\_act\*\*2 + var\_pla\*\*2 - 2\*(4\*act\*pla\*cov\_ACT + var\_act\*var\_pla));

Type of document Document ID	Date: Version: Status:	11-Aug-2022 4.0 Final	
INTERNAL USE	Page:	58 of 79	

### 7.2.5 SAS code for the analysis

#### SAS Code for the Primary Efficacy Endpoint

The term region in the code below refers to the definition of region in section 4.1.1.

#### SAS Code

proc genmod data=a;

class treat agegroup region;

model aval = treat agegroup region/ link=log dist=negbin offset=log\_time;

Ismeans treat/ cl means exp diff ;

run;

/pe of document ocument ID	Date: Version:	ate: 11-Aug-2022 ersion: 4.0	
	Status:	Final	
INTERNAL USE	Page:	59 of 79	

# 7.3 Appendix 3: Preferred terms

#### 7.3.1 Asthma

PTs to identify asthma exacerbations, asthma related hospitalisations, worsening of asthma requiring medication and asthma related symptoms leading to IMP discontinuation have been selected by using the following criteria (MedDRA version 20.1):

Standardised MedDRA Query (SMQ) Asthma/bronchospasm

PTs for identification of asthma
Aspirin-exacerbated respiratory disease
Asthma
Asthma exercise induced
Asthma late onset
Asthma-chronic obstructive pulmonary disease overlap syndrome
Asthmatic crisis
Bronchial hyperreactivity
Bronchospasm
Infantile asthma
Occupational asthma
Reactive airways dysfunction syndrome
Severe asthma with fungal sensitisation
Status asthmaticus
Airway remodelling
Allergic bronchitis
Allergic cough
Allergic eosinophilia
Allergic respiratory disease
Allergic respiratory symptom
Alveolitis allergic
Bronchial obstruction
Bronchospasm paradoxical
Charcot-Leyden crystals
Forced expiratory flow decreased
Forced expiratory volume decreased

Type of document Document ID	Date: Version:	11-Aug-2022 4.0 Final	
INTERNAL USE	Page:	60 of 79	

PTs for identification of asthma
Fractional exhaled nitric oxide abnormal
Fractional exhaled nitric oxide increased
Functional residual capacity increased
Hyperventilation
Hypocapnia
Нурохіа
Lung hyperinflation
Lung hypoinflation
Obstructive airways disorder
PCO2 decreased
Peak expiratory flow rate abnormal
Peak expiratory flow rate decreased
PO2 decreased
Prolonged expiration
Pulmonary sensitisation
Respiratory alkalosis
Reversible airways obstruction
Tachypnoea
Wheezing

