11.19 Asthma Action Plan

An Asthma Action Plan will be given to the subjects and parents/caregivers to provide guidance to effectively manage the subject's symptoms, as recommended by clinical practice guidelines. Subjects will be trained in their Asthma Action Plan by the investigator or designee. According to the Asthma Action Plan, subjects must contact the investigator when asthma symptoms increase or in cases with reduction in lung function. Signs and symptoms of asthma worsening include:

- Cough, wheeze, chest tightness or shortness of breath, or
- Waking at night due to asthma, or
- Can do some, but not all, usual activities, or
- Increased need for reliever medication, or
- Peak flow 50-79% of personal best

The investigator or designee will fill in the appropriate treatment for the subjects in the Asthma Action Plan.

The subject is instructed to call an ambulance while taking reliever medication at regular intervals as pre-specified by the investigator for serious situations when the subjects experience that:

- Symptoms worsens very quickly
- Wheeze, chest tightness or shortness of breath continue after taking reliever medication, or
- There is severe shortness of breath, inability to speak comfortably, blueness of lips, or
- Peak flow is below 50% of personal best

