12.3 Collection, recording and reporting of adverse events

At each contact with the trial site, the subject must be asked about AEs in an objective manner such as "Have you experienced any problems since the last contact?"

AEs must be recorded on the AE form in the eCRF. One single AE form must be used per AE from start to resolution. For SAEs and ESIs, specific SAE and ESI data fields in the eCRF must also be filled in.

If the same type of AE occurs more than 1 day in a row with the same pattern (e.g. itching in the mouth for 5-10 minutes after intake of IMP) it is considered a recurrent AE. The AE form should be filled in with the start date and the description. Once the AE no longer reccurs after IMP intake, the AE form should be completed with a stop date. If the AE then re-appears on a subsequent day, a new AE form should be filled in.

The investigator should record the diagnosis, if available. If no diagnosis is available the investigator should record each sign and symptom as individual AEs. Further, the diagnosis of the underlying disease should be reported instead of a procedure performed due to the disease (e.g. if a subject undergoes surgery due to appendicitis, appendicitis, and not the surgery performed, should be reported as the AE).

Solicited Adverse Events

The eDiary will be used to capture 15 specific symptoms, identified as local side effects of sublingual immunotherapy (Passalacqua et al. 2013). These local side effects will be collected on a daily basis by the subject during the first 28 days of treatment (Section 11.21). The eDiary is to be completed by the subject/parent/caregiver. Subjects or their parent/caregiver will be trained by the investigator or designee at visit 3 on the proper method to complete the eDiary. The reported symptoms will be evaluated by investigator and reported in the eCRF as AEs on the AE form in the eCRF.

The duration in minutes of the solicited AEs occurring on Day 1 (visit 3) will be collected. The AE start and stop time of solicited AEs that occur on Day 1 within 60 minutes of IMP intake, will be monitored by site personnel, recorded in source documents, and entered into the eCRF. After Day 1, standard AE reporting conventions will be utilised, as described above. For more details on solicited AEs, please see Section 11.21.

Eosinophilic Oesophagitis

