15.9 Safety analyses

Analyses of AEs

AEs are recorded from the subjects sign the informed consent and until the last follow-up visit.

Unless otherwise specified, AE endpoints in this protocol refer to events occurring after the first IMP administration (treatment-emergent AEs).

AEs will be summarised by treatment group, MedDRA system organ class (SOC) and preferred term (PT) displaying number of subjects in treatment group, number and percentage of subjects having the event as well as number of events. Furthermore, the AEs will be summarised according to severity, relationship, outcome and seriousness.

Additionally the following AEs will be summarised by treatment group

- asthma exacerbations
- asthma related hospitalisations
- worsening of asthma requiring medication
- discontinuations of treatment due to asthma related symptoms
- solicited AEs
- unsolicited adverse events

The analyses will be described further in the SAP.

Analyses of other safety parameters

Physical examination assessments, laboratory assessments, vital signs and FEV_1 will be summarised by means of descriptive statistics.

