TEAEs leading to IMP interruptions, serious TEAEs (SAEs) and TEAEs leading to IMP discontinuations will be summarised by SOC, PT and treatment group in separate tables. A cumulative incidence plot will be used to show the cause specific distribution of IMP discontinuation due to TEAEs.

Most frequent TEAEs are those AEs (defined as MedDRA PTs) that are present in at least 2% of subjects with active treatment. Most frequent TEAEs and most frequent IMP-related AEs will be summarised by SOC, PT and treatment group in separate tables.

Additionally, the following TEAEs will be summarised by treatment group displaying the number and frequency of subjects having the event as well as number of events, see **0** (Appendix 3: Preferred Terms):

- asthma related events
- asthma related hospitalisations

Type of document	Date:	11-Aug-2022	
Document ID	Version:	4.0	
	Status:	Final	
INTERNAL USE	Page:	40 of 79	

Κ

- worsening of asthma requiring medication
- asthma related symptoms leading to IMP discontinuation
- solicited TEAEs
- TEAEs excluding solicited events and clinically relevant asthma exacerbations

Onset of a TEAE is defined as time (e.g. minutes or days) from first IMP intake to start of the first TEAE of a given PT. An onset of 1 day means that the TEAE has started on the day of first IMP intake.

Resolution time of a TEAE is defined as days from start of the TEAE until the TEAE is resolved, e.g., recurrent TEAEs like oral pruritus that occurs every day for 1 minute on 5 days in a row will have a resolution time of 5 days.

Resolution time and onset in minutes/hours/days will be summarised by treatment group for most frequent TEAEs and for local application site TEAEs displaying mean, SD, median, 5% percentile, 95% percentile, minimum and maximum.

For solicited TEAEs the duration in minutes on the first day of IMP intake will be summarised.

All AEs will be listed including non-TEAEs.

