#### 7.1.2.7 The average asthma DSS

Asthma symptoms are recorded daily during the periods with eDiary recording.

The asthma symptoms consist of 4 asthma symptoms (cough, wheezing, chest tightness and shortness of breath) which are scored from 0 to 3 as follows:

- 0 = no symptoms
- 1 = mild symptoms
- 2 = moderate symptoms
- 3 = severe symptoms

The asthma DSS is the sum of all 4 individual asthma symptom scores and ranges from 0 to 12.

The average asthma DSS is for each subject and each visit (V2, V5, V6, V7, V8, V9, V10, V11) calculated as the average of non-missing records during the 14 days of eDiary assessment.

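### The safety row on asthma related symptoms leading to IMP discontinuation has no term for shortness of breath, chest tightness or plain cough, so stops recorded only as one of these are missed in that row

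*SAP*

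**What the plan says.** Protocol section 15.9 plans a summary by treatment group of "discontinuations of treatment due to asthma related symptoms". SAP section 4.5.2 carries it forward as "asthma related symptoms leading to IMP discontinuation" and sends the reader to Appendix 3 for the terms.

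Appendix 3, section 7.3.1, uses a single list for this row and three others: "PTs to identify asthma exacerbations, asthma related hospitalisations, worsening of asthma requiring medication and asthma related symptoms leading to IMP discontinuation have been selected". The only selection criterion is "Standardised MedDRA Query (SMQ) Asthma/bronchospasm", in MedDRA version 20.1.

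The trial's asthma symptoms are set out elsewhere. SAP section 7.1.2.7 says: "The asthma symptoms consist of 4 asthma symptoms (cough, wheezing, chest tightness and shortness of breath". Protocol Table 11 scores the same four. The Asthma Action Plan in protocol section 11.19 lists them among the signs of worsening: "Cough, wheeze, chest tightness or shortness of breath".

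On recording, protocol section 12.3 asks for the diagnosis first, and then: "If no diagnosis is available the investigator should record each sign and symptom as individual AEs".

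**The concern.** A list headed as identifying asthma is used for a row labelled as asthma related symptoms. It reaches well beyond diagnoses (*Hypocapnia*, *Respiratory alkalosis*, *Charcot-Leyden crystals*), yet it leaves out most of the symptoms that the trial asks families to report.

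The row has a purpose. Protocol section 12.1 says that exacerbations are not a safety endpoint unless they are serious. Respiratory symptoms below that threshold which lead a child to stop are what this row should gather into one by-arm count. The solicited-event list in SAP section 7.3.3 contains none of the missing symptoms. If the row reads low against its own label, a reader of the report could take it as a complete count when it is not.

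**Working it through.** No sample-size or test figure is involved. The check compares the printed list with the symptoms.

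**Inputs.** The 44 preferred terms in SAP section 7.3.1, and the four asthma symptoms in SAP section 7.1.2.7, protocol Table 11 and protocol section 11.19.

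**Search of the 44 terms for each symptom.**

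| Trial symptom | Strings searched | Matches |
|---|---|---|
| Wheezing | wheez | *Wheezing* |
| Cough | cough | "Allergic cough" only |
| Chest tightness | chest, tight, discomfort | none |
| Shortness of breath | dysp, breath, shortness | none |

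One of the four symptoms is fully covered. Cough is covered only when coded as allergic. Two have no term at all.

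**Is this a loss in reading the PDF?** It does not look like one. The list is two blocks of 13 and 31 terms (13 + 31 = 44), each in alphabetical order. Terms beginning with cough, chest or dysp would fall between *Charcot-Leyden crystals* and *Forced expiratory flow decreased*. These two terms are adjacent on the same page, so the gap is not at a page break.

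**What follows for one child who stops the tablet:**

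- Event recorded as asthma or bronchospasm: counted in the row.
- Event recorded as wheezing, without a diagnosis: counted.
- Event recorded as shortness of breath, chest tightness or plain cough, without a diagnosis: not counted in the row.
- In all three cases the event appears in the table of TEAEs leading to IMP discontinuation, by SOC, preferred term and treatment group (SAP section 4.5.2).

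The primary endpoint is not touched. It is derived from the exacerbation criteria on the AE form (SAP section 7.1.1.1), not from this list.

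**The case against.** The strongest reply has four parts.

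1. **The events are reported elsewhere.** Besides the discontinuation table by SOC and preferred term, SAP section 4.5.2 plans a cumulative incidence plot of discontinuation due to TEAEs and a listing of all AEs. Section 6.1 adds disposition by primary reason. This stands: nothing is lost from the report. What that table does not give is one by-arm count of children across the asthma symptom terms, which is what the dedicated row offers.

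2. **Symptom-only records should be the exception.** Protocol section 12.3 puts the diagnosis first. Every child has physician-diagnosed asthma of at least one year (inclusion criterion I4), and section 12.1 treats worsening of a pre-existing condition as an AE. Symptoms that the investigator attributes to asthma should normally be recorded as asthma, which is on the list. This also stands, and it narrows the gap to symptoms recorded without a diagnosis.

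3. **A standard query is a defensible choice.** It is prespecified and reproducible, and the four symptoms come from an eDiary score and an action plan, not from a rule for grouping AEs. That supports keeping the SMQ count. It does not make the row's label accurate.

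4. **Adding terms costs specificity.** Protocol section 11.20 lists shortness of breath, cough and wheezing among systemic reactions, and throat irritation is a known local effect. Added terms could bring such reactions, or infections, into an asthma row. This is fair, and it is why the wider count should be supplementary and shown by term.

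A reader might also infer that three of every four asthma-related stops (75%) are missed. The documents do not support that. The share missed is s × u, where s is the share of asthma-related stops recorded only as symptoms and u is the share of those that are one of the three uncovered symptoms. Neither is given. Assuming u = 0.75 (equal reporting of four symptoms), s = 1 gives 75%, s = 0.5 gives 37.5% and s = 0.1 gives 7.5%. The 75% needs s = 1, meaning that no stop was ever recorded as asthma.

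**Conclusion.** The point holds for one descriptive row. As defined, the row cannot count a stop recorded only as shortness of breath, chest tightness or plain cough, although its label covers them. This rests on the printed list being complete, which its order supports.

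The number of children affected cannot be determined, because the documents give no counts and no split between diagnosis-coded and symptom-coded stops. Nor can the direction. A reader might infer that the undercount falls mainly on the active arm and makes the tablet look safer. That would require the tablet to provoke these symptoms as asthma and investigators to record them without a diagnosis. The documents establish neither, and they list shortness of breath and cough as possible systemic allergic reactions as well.

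No hypothesis test, primary result or other safety table changes. Priority is minor.

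**What to change.** In SAP section 7.3.1, for this row only:

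- Keep the existing count and label it as Asthma/bronchospasm SMQ events leading to IMP discontinuation.
- Beside it, add a supplementary count that also includes the MedDRA 20.1 preferred terms to which shortness of breath, chest tightness and cough code. The sponsor should confirm the exact terms, since the documents do not show them.
- Show the supplementary count by preferred term and treatment group, with a note that the added terms are less specific and may include infections or local or systemic allergic reactions.
- Leave the exacerbation, hospitalisation and worsening-requiring-medication rows unchanged.

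If the data are already unblinded, mark the added count as post hoc, in line with protocol section 15. The cost is a line in Appendix 3, a relabelled row and one rerun table. The loss of specificity is confined to the supplementary count, where the breakdown by term makes it visible.

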# 7.3.2 Local application site TEAEs

PTs related to local application site TEAEs have been selected by using the following criteria (MedDRA version 20.1):

High-Level Group Terms (HLGTs)
Oral soft tissue conditions
Salivary gland conditions
Tongue conditions
High-Level Terms (HLTs)
Gingival disorders NEC
Gingival discolourations
Gingival haemorrhages
Gingival pains

Type of document Document ID INTERNAL USE	Date: Version: Status: Page:	11-Aug-2022 4.0 Final 61 of 79	ALK
---	---------------------------------------	---	------------

Type of document Document ID	Date: Version:	11-Aug-2022 4.0	
	Status:	Final	
INTERNAL USE	Page:	62 of 79	

### 7.3.3 Solicited adverse events

PTs related to solicited TEAEs are listed below

PTs for identification of solicited TEAEs
Dysgeusia
Taste disorder
Mouth ulceration
Enlarged uvula
Oedema uvula
Palatal swelling
Palatal oedema
Mouth swelling
Oedema mouth
Oral pruritus
Ear pruritus
Lip swelling
Lip oedema
Swollen tongue
Tongue oedema
Glossodynia
Tongue ulceration
Throat irritation
Pharyngeal oedema
Pharyngeal swelling
Abdominal pain upper
Abdominal pain
Nausea
Vomiting
Diarrhoea

Type of document Document ID	Date: Version:	11-Aug-2022 4.0	
	Status:	Final	
INTERNAL USE	Page:	63 of 79	

Page 16 of 16

Type of document	Date:	11-Aug-2022	
Document ID	Version: 4.0 Status: Final	4.0	
INTERNAL USE	Page:	79 of 79	

